2.2.3 Immunogenicity

Serum blood samples will be taken pre-dose on Day 0, and Weeks 2, 4, 8, 12 (pre-dose), 24 (pre-dose), 36 (pre-dose), 48 (pre-dose), 72 (pre-dose), and 104 or ET to test for the development of antibodies to ALD403. The immunogenicity will be assessed in serum from all ALD403-treated subjects using a validated assay.

For any samples that are positive for anti-ALD403 antibody, there may be additional testing to characterize the anti-ALD403 antibody for the potential to neutralize (NAb) ALD403 activity. Subjects who test positive for specific anti-ALD403 antibodies at the time of the last study visit will be asked to provide up to 2 additional blood samples for immunogenicity testing at 3 month intervals for up to 6 months.

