2.3 Trial Day

Trial endpoints will be reported within analysis windows based upon the actual date of the assessment. Assignment of results to these time points is based upon the trial day. Trial day is defined as:

Trial day = date of assessment - date of treatment

Analysis Windows used to report endpoints are outlined in [Table 2](#)

TABLE 2: ANALYSIS WINDOWS

Visit	Range	Target Day	If more than one which one is used for analyses
Screening	< Day 0		First value
Day 0	Day 0 to Day 7	Day 0	Closest to Target Day
Week 2	Day 8 to Day 21	Day 14	Closest to Target Day
Week 4	Day 22 to Day 42	Day 28	Closest to Target Day
Week 8	Day 43 to Day 70	Day 56	Closest to Target Day
Week 12	Day 71 to Day 126	Day 84	Closest to Target Day
Week 24	Day 127 to Day 204	Day 168	Closest to Target Day

Week 36	Day 205 to Day 288	Day 252	Closest to Target Day
Week 48	Day 289 to Day 378	Day 336	Closest to Target Day
Week 60	Day 379 to Day 462	Day 420	Closest to Target Day
Week 72	Day 463 to Day 546	Day 504	Closest to Target Day
Week 84	Day 546 to Day 630	Day 588	Closest to Target Day
Week 104	> Day 630	Day 728	Closest to Target Day

Note: If two observations are equidistant to the target day, the first observation is used.

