3.6.5 Immunogenicity Data Analysis

Analyses will be conducted for safety population. Analysis of specific anti-ALD403 antibodies is restricted to subjects who are treated with ALD403.

For subjects with pre-existing antibodies at baseline, the number and percent of subjects who are positive for anti-ALD403 antibody will be summarized. In addition, the number and percent of subjects who develop anti-drug antibodies to ALD403 during the trial will be summarized at each scheduled visit in the same table. Denominators for percentages will be the total number of results available for the specified visit.

All the immunogenicity data will be listed.

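### Extra antibody samples taken only from subjects positive at their last visit are not kept out of the by-visit windows, so they can distort the Week 72 rate and create a spurious Week 84 row

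*SAP*

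**What the plan says.** Four provisions combine.

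- **Windowing (SAP 2.3).** "Trial endpoints will be reported within analysis windows based upon the actual date of the assessment", and "Assignment of results to these time points is based upon the trial day". Table 2 gives Week 60 as "Day 379 to Day 462" and Week 72 as "Day 463 to Day 546". Week 84 runs from Day 546 to Day 630, and Week 104 is everything after Day 630. Where a subject has several results in a window, the one closest to the target day is used. There is no Week 56 row and no exclusion for results obtained after the End-of-Trial visit.
- **Extra samples (SAP 2.2.3; also Protocol 12.3 and footnote 6 of the Schedule of Events).** Subjects positive for anti-ALD403 antibodies at their last visit "will be asked to provide up to 2 additional blood samples for immunogenicity testing at 3 month intervals for up to 6 months". Negative subjects are not asked.
- **Antibody table (SAP 3.6.5).** Antibody development is tabulated by scheduled visit. "Denominators for percentages will be the total number of results available for the specified visit". All immunogenicity data are also listed.
- **Who ends when (SAP 1.2 and Table 1).** Subjects who miss a primary-phase infusion or decline the secondary phase end at Week 56, Day 392 ± 7. The others end at Week 104, Day 728 ± 7. Late in the trial, antibody samples are scheduled at Weeks 48 and 72 and at end of trial or early termination. None is scheduled at Week 60 or Week 84 (Protocol Section 2; SAP 2.2.3).

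**The concern.** The extra samples are selected on the outcome being tabulated, because a subject gives one only after testing positive. If they enter a by-visit percentage, they add mostly positive results to the numerator, and nothing comparable enters the denominator from the negative subjects who left at the same time. The closest-to-target rule does not remove them for Week 56 finishers, who have no other antibody sample in the Week 72 or Week 84 window.

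These subjects are also long past dosing. Their last possible primary-phase infusion is Week 36 (Day 252), so a retest near Day 483 comes about 483 - 252 = 231 days later. It would sit beside scheduled pre-dose samples from the secondary treatment phase.

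Immunogenicity of repeat doses is a secondary objective and antibody development is a listed endpoint. An artefact at Weeks 72 and 84 could be read as immunogenicity rising with later infusions.

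**Working it through.** **The plan's own figure.** The documents give no antibody rate, persistence or uptake. The one related number is the sample-size statement (SAP 1.3): 120 × 0.75 = 90, which reproduces.

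**Step 1: where the extra samples fall.** Trial day is taken from the first dose, and 3 months as 84 to 92 days. Sample day = last-visit day + one or two intervals.

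- Week 56 exit, Days 385-399, first extra: 385 + 84 = 469 to 399 + 92 = 491. This is always inside Week 72 (463-546).
- Week 56 exit, second extra: 385 + 168 = 553 to 399 + 184 = 583. This is always inside Week 84 (546-630).
- Week 104 completers: 721 + 84 = 805 to 735 + 92 = 827, then 721 + 168 = 889 to 735 + 184 = 919. All fall in the open Week 104 window but lose to the sample taken at about Day 728, if it exists.
- Early withdrawals depend on timing:

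| Last visit | First extra | Second extra |
|---|---|---|
| Week 12 | Week 24 | Week 36 |
| Week 24 | Week 36 | Week 48 |
| Week 36 | Week 48 | Week 60 |
| Week 48 | Week 60 | Week 72 |
| Week 60 | Week 72 | Week 84 |
| Week 72 | Week 84 | Week 104 |
| Week 84 | Week 104 | Week 104 |

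**Step 2: what is in the Week 60 row.** The routine End-of-Trial sample of Week 56 finishers (Days 385-399) lies inside Days 379-462. It is taken whatever the antibody status. Their extra samples never reach this window.

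**Step 3: size at Week 72.** Let S = scheduled Week 72 samples, E = Week 56 exits, p = true rate (the same in both groups), u = uptake of the extra sample, and q = share of retests still positive.

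Reported rate = (S·p + E·p·u·q) / (S + E·p·u)

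All inputs are assumptions. With S = 80, p = 10% and u = 1:

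| q | E = 20 | E = 30 |
|---|---|---|
| 1 | (8 + 2)/82 = 12.2% | (8 + 3)/83 = 13.3% |
| 0.5 | (8 + 1)/82 = 11.0% | (8 + 1.5)/83 = 11.4% |
| 0.1 (= p) | (8 + 0.2)/82 = 10.0% | (8 + 0.3)/83 = 10.0% |
| 0 | 8/82 = 9.8% | 8/83 = 9.6% |

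The rate rises only if q > p. Other cases:

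- Half uptake and half persistence, E = 20: (8 + 0.5)/81 = 10.5%.
- p = 20%, q = 1, u = 1: (16 + 4)/84 = 23.8% for E = 20 and (16 + 6)/86 = 25.6% for E = 30.
- S = 90 and E = 30 (from the 75% assumption), p = 10%, u = 1: 12/93 = 12.9% for q = 1 and 10.5/93 = 11.3% for q = 0.5.
- S = 60 and E = 60 (many subjects not entering the secondary phase), p = 10%, u = 1: 12/66 = 18.2% for q = 1 and 9/66 = 13.6% for q = 0.5.

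**Step 4: Week 84.** With no scheduled sample, the row would hold the second retests plus any early-withdrawal sample that happens to fall in Days 546-630. Its percentage would be close to q, whatever the true rate.

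**The case against.** The strongest reply is that SAP 3.6.5 speaks of antibodies developing in the course of the trial and of scheduled visits. The extra samples come after the last study visit, have no column in the Schedule of Events and are voluntary, so a sensible programmer would leave them out. That reading is possible, but the SAP does not state it. Weeks 72 and 84 are scheduled visits, Table 2 is the rule that maps results to them, and that rule uses only the date. Listing all the data does not keep any of it out of the table.

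Other parts of the reply stand. A reader might infer that the antibody rate is inflated at Weeks 60, 72 and 84 as a matter of course. The documents do not support that:

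- **Week 60** would mainly hold unselected Week 56 samples. Extra samples reach it only after early withdrawal, and two of the four withdrawal reasons in Protocol 8.4.2 (withdrawn consent, loss to follow-up) make later voluntary samples unlikely.
- **Week 84** has no planned rate to inflate, and its row need not consist only of retests, because early-termination samples can fall there too.
- **Week 72** rises only if the samples are windowed, subjects agree to give them, and retest positivity exceeds the true rate. The SAP does not label the table an on-treatment rate.

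The table is also descriptive. No antibody test or decision rule depends on it, and the listing leaves dates and subjects visible.

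**Conclusion.** The point holds as a missing exclusion rule. Applied as written, the SAP mixes samples selected for positivity with scheduled samples at Week 72 and can produce a Week 84 row that no planned sample supports. Early withdrawals can do the same in other windows.

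Under the base assumptions the Week 72 error is about 1 to 3 percentage points on a true 10%, and nil or slightly negative if retests are no more often positive than the true rate. It grows if many subjects do not enter the secondary phase, a number the documents do not give. All sizes rest on assumed antibody rate, persistence, uptake and numbers of exits, on equal rates in both groups, and on 84- to 92-day intervals. The consequence is modest, but the correction is cheap and should be made before the table is programmed.

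**What to change.** In SAP 2.3 and 3.6.5:

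1. State that antibody samples taken after a subject's End-of-Trial/Early Withdrawal visit are not assigned to Table 2 windows and do not count in by-visit numerators or denominators.
2. Report them separately as persistence or resolution, by months since the last visit, with subjects positive at that visit as the denominator.
3. Limit by-visit antibody rows to visits with a scheduled sample.
4. Report the Week 56/early-withdrawal End-of-Trial sample in its own row, so that it does not appear under Week 60 or another nominal visit.

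With S = 90, E = 30, p = 10% and full uptake and persistence, the first change returns Week 72 from 12/93 = 12.9% to 9/90 = 10.0%. The cost is a few sentences and a programming flag. No new data are needed, and the extra samples remain in the listing.

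### SAP Table 2 puts Day 546 in two visit windows, and its Week 24/36 and Week 36/48 cuts (Days 204 and 288) break the pattern of the other 12-week boundaries

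*SAP*

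**What the plan says.** SAP section 2.3 makes Table 2 the rule for placing results at visits: "Assignment of results to these time points is based upon the trial day". The same section counts days by a one-line formula, "Trial day = date of assessment - date of treatment". I take the treatment date to be that of the first infusion, since the target days make sense only on that reading.

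The Table 2 ranges that matter here are:

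- Week 24 (target Day 168): "Day 127 to Day 204"
- Week 36 (target Day 252): "Day 205 to Day 288"
- Week 48 (target Day 336): "Day 289 to Day 378"
- Week 60 (target Day 420): "Day 379 to Day 462"
- Week 72 (target Day 504): "Day 463 to Day 546"
- Week 84 (target Day 588): "Day 546 to Day 630"

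Week 104 (target Day 728) takes everything after Day 630. If a window holds several results, the one closest to the target day is used. A note adds that, of two results equally far from a target, the first is taken. The SAP does not state how the range limits were chosen.

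**The concern.** Analysis windows should send each result to one visit. Day 546 is sent to two. With no rule to break the overlap, two programmers could produce different Week 72 and Week 84 tables from the same data.

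The 204 and 288 limits raise a different question. They look like slips in a table that is otherwise regular. A result just after either limit is carried to a visit whose target is farther away. It then competes with that visit's own result and, under the closest-to-target rule, normally loses. Because summaries use observed data only (SAP 2.6.1), the value then leaves the by-visit table and the earlier visit may be left empty.

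The windows govern the by-visit summaries of questionnaires, laboratory values, vital signs, ECG, drug concentrations and antibodies (SAP 3.4 to 3.6). They also feed the t-tests on SF-36, HIT-6 and MIDAS changes (SAP 3.4.2, 3.4.5, 3.4.6).

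**Working it through.** **Inputs.** Target days and range limits are from SAP Table 2. Protocol visit windows are from the Schedule of Events (protocol section 2; SAP Table 1).

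**Step 1: coverage.** With every day placed in its printed range or ranges, no day is left uncovered and exactly one day, 546, is in two windows. Its distances are 546 − 504 = 42 and 588 − 546 = 42, so distance to target cannot decide between them. The tie note does not help either: it chooses between two results competing for one target, whereas here one result faces two targets.

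**Step 2: the 12-week boundaries.** Two candidate rules are the midpoint of adjacent targets, (T₁ + T₂)/2, and a fixed half-width, T₁ + 42. Targets 84 days apart give the same answer under both.

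| Boundary | Midpoint | T₁ + 42 | Printed upper limit |
|---|---|---|---|
| Week 12/24 | (84 + 168)/2 = 126 | 126 | 126 |
| Week 24/36 | (168 + 252)/2 = 210 | 210 | **204** |
| Week 36/48 | (252 + 336)/2 = 294 | 294 | **288** |
| Week 48/60 | (336 + 420)/2 = 378 | 378 | 378 |
| Week 60/72 | (420 + 504)/2 = 462 | 462 | 462 |
| Week 72/84 | (504 + 588)/2 = 546 | 546 | 546 |

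Four of the six printed limits are reproduced. The other two are each 6 days short. The earlier limits (7, 21, 42, 70) are also midpoints.

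**Step 3: days affected by the two short limits.**

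| Day | Distance to earlier target | Distance to later target | Printed assignment |
|---|---|---|---|
| 205 | 205 − 168 = 37 | 252 − 205 = 47 | Week 36 |
| 209 | 41 | 43 | Week 36 |
| 210 | 42 | 42 | Week 36 (tie) |
| 289 | 289 − 252 = 37 | 336 − 289 = 47 | Week 48 |
| 293 | 41 | 43 | Week 48 |
| 294 | 42 | 42 | Week 48 (tie) |

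Days strictly nearer the earlier target but assigned to the later visit are 205-209 and 289-293, 5 + 5 = 10 days. Days 210 and 294 are exact ties; elsewhere in the table such ties (126, 378, 462) go to the earlier visit.

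**Step 4: can a scheduled visit land on these days?** The protocol windows are Week 24, Days 165-171; Week 36, 249-255; Week 48, 329-350; Week 56, 385-399; Week 60, 413-427; Week 72, 497-511; Week 84, 581-595; Week 104, 721-735. None contains an affected day. An early-termination visit (protocol 8.4.2.2), an unscheduled assessment or a badly delayed visit can.

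**Step 5: what happens to such a result.**

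- A delayed Week 24 assessment on Day 205 enters the Week 36 window at distance 47. An on-time Week 36 result, at most 3 days from target, displaces it, and Week 24 has no value.
- A withdrawal visit on Day 205 with no later result is reported as Week 36, 47 days before that target.
- A Day 546 result appears at both Week 72 and Week 84 only if the subject has no closer result in either window.

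**The case against.** The strongest reply is that the SAP never adopts a midpoint or nearest-target rule. Results go where the printed ranges send them, and closeness only chooses among results already inside a window. On that view only Day 546 is an internal contradiction, and 204 and 288 are merely unexplained. This stands in part: the pattern is inferred. But neither rule that explains the neighbouring limits yields 204 or 288, and the SAP offers no other reason for them.

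A second reply is that the closest-to-target rule removes most of the practical effect. That also stands. An on-time visit displaces any of these stray results, so a reported value changes only where a nearer result is missing or a stray value is lost. Adverse event incidence, laboratory values out of range at any time after baseline, and the C-SSRS ever-yes summary do not depend on the windows.

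A reader might go further and infer that the Week 84/104 cut at Day 630 is also wrong, because the midpoint is (588 + 728)/2 = 658 and Days 631-657 are nearer Week 84. The documents do not support that. The limit equals 588 + 42, the half-width that fits the neighbouring visits, and it is a defensible stop before a gap of 728 − 588 = 140 days. Moving it to 658 would stretch Week 84 to 70 days after its target. For drug concentration and antibody samples, SAP 2.2.2 and 2.2.3 group early termination with Week 104 and plan no Week 84 sample, so a withdrawal sample on those days belongs where it now falls.

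Nor should affected days be quoted as a share of the trial calendar: that is not a share of the data. Double reporting is possible on Day 546 alone.

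**Conclusion.** The point holds as a minor drafting error. The Day 546 overlap is wrong under any rule. The 204 and 288 limits are irregular by 6 days each and send ten days' results to the farther visit. This second part assumes that the pattern of the other 12-week boundaries was intended throughout.

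The documents do not show how many assessments will fall on these days, so the effect on results cannot be quantified. It is probably small: visits held within protocol windows are untouched and the study is mainly descriptive. The case for correcting the table is that each result should have one visit, fixed in advance.

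**What to change.** In SAP Table 2, change four ranges:

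- Week 24: Day 127 to Day 210
- Week 36: Day 211 to Day 294
- Week 48: Day 295 to Day 378
- Week 84: Day 547 to Day 630

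Leave the Day 630 limit and the Week 104 row as they are. If 204 and 288 were deliberate, keep them and state the reason in section 2.3; the Week 84 start must change either way. With these edits no day is in two windows, and each window from Week 24 to Week 84 runs from 41 days before its target to 42 days after it.

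One consequence should be accepted knowingly: a withdrawal result on Days 205-210 or 289-294 will fall in the earlier window and give way to an on-time result there, so the later visit will have no value for that subject.

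The cost is four cells of one table, with no change to conduct or data collection. It is best settled before the interim analysis in SAP 2.6.3, which uses the Week 24 to Week 48 windows. The edit does not address the scheduled Week 56 end-of-trial visit, which has no row in Table 2 and falls in the Week 60 window; that is a separate matter.

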1.3 Sample Size

The planned sample size for this study is 120 treated subjects. It is assumed that over 75% of these subjects will complete the primary treatment phase resulting in at least 90 subjects with one year of safety data collection.

TABLE 1: SCHEDULE OF EVENTS AND ASSESSMENT

Assessments	Screening Day -14 to -11	Day 0	Wk 2 Day 14 ± 3 days	Wk 4 Day 28 ± 3 days	Wk 8 Day 56 ± 3 days	Wk 12 & 24 & 36 Day 84 / 168 / 252 ± 3 days	Wk 48 Day 336 -7/+14 days	Wk 60 & 72 & 84 Day 420 / 504 / 588 ± 7 days	Wk 56 ⁹ or 104 EOT / Early Withdrawal Day 392 or 728 ± 7 days
Informed Consent, Demographics, Medical History, Height	X								
In/Ex Criteria	X	X							
Weight	X	X				X			X
Physical Exam ¹	X	X				X	X ¹¹	X	X
Vital Signs ³	X	X				X	X	X	X
C-SSRS ^{4,1}	X	X	X	X	X	X	X	X	X
PGIC ²				X	X	X	X	X	X
SF-36, HIT-6 ¹	X	X		X		X	X	X	X
EQ-5D-5L ¹²	X	X		X		X	X		X ¹⁰
MBS	X	X		X	X	X	X		X ¹⁰
MIDAS ¹		X				X	X	X	X
AE/ Con Med Review	X	X	X	X	X	X	X	X	X
ALD403 infusion ⁵		X				X	X ¹¹	X	
12-lead ECG ⁷	X	X				X	X	X	X
Hematology, Chemistry ¹	X	X				X	X	X	X
HIV/Hepatitis B and C	X								
Plasma PK ^{6,8}		X	X	X	X	X	X		X
Serum Anti-ALD403 ⁶		X	X	X	X	X	X		X
Urine Drugs of Abuse ¹	X								
Urine Pregnancy Test	X	X		X	X	X	X	X	X

¹ Conduct assessment pre-dose on Day 0 and Week 12, 24, 36, 48, 60, 72, and 84.

² Conduct assessment pre-dose on Week 12, 24, 36, 48, 60, 72, and 84.

³ Conduct assessments pre-dose and up to 2 hours (+ 30 min) post-dose on Day 0 and Week 12, 24, 36, 48, 60, 72, and 84.

⁴ Conduct **C-SSRS Baseline/Screening Version** at screening and **C-SSRS Since Last Visit Version** at remaining visits where C-SSRS required.

⁵ Monitor subjects for at least 2 hours after the end of each dosing to assess for the occurrence of adverse events.

⁶ Collect samples pre-dose on Day 0 and Week 12, 24, 36, 48, and 72. Subjects who test positive for anti-ALD403 antibodies at the last study visit will be asked to provide up to 2 additional blood samples for immunogenicity testing at 3 month intervals for up to 6 months.

⁷ Conduct assessment pre-dose, and within 2 hours (+ 30 min) post dose on Day 0 and Week 12, 24, 36, 48, 60, 72, and 84.

⁸ On Day 0, collect additional sample immediately post-dose (within 15 minutes of end of infusion).

⁹ Subjects who don't received all 4 infusions of ALD403 in the primary treatment phase or don't consent to participate in the secondary treatment phase will have the End of Trial/Early Withdrawal visit at Week 56.

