3.2 Definition of Baseline

The baseline assessment will be the latest available valid measurement taken prior to the administration of Investigational Product. This will generally be Day 0.

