3.6.4 Vital Signs, Physical Findings and Other Observations Related to Safety

3.6.4.1 Vital Signs

The observed data at baseline and change from baseline for each measurement day will be summarized with descriptive statistics. A plot of average vital sign parameters will be presented over time.

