3.6.4.3 Electrocardiogram Results

The observed data at baseline and change from baseline for each measurement day will be summarized with descriptive statistics.

The overall ECG interpretation based on investigator interpretation will be summarized including post treatment ECGs determined to be abnormal clinically significant.

The absolute QTcF values provided by the core lab will be analyzed as a categorical variable. Each QTcF value in a given patient will be grouped into 4 categories:

- QTcF interval < 450 msec
- QTcF interval 450 - 480 msec
- QTcF interval > 480 - 500 msec
- QTcF interval > 500 msec

The changes in QTcF measures will also be analyzed as categorical variables. The change in QTcF in a given patient will be grouped into 2 categories:

- QTcF interval increases from baseline > 30 msec
- QTcF interval increases from baseline > 60 msec

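### Read literally, the visit-window tie rule drops every same-day post-infusion vital sign and ECG from the by-visit mean-change summaries

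*SAP*

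**What the plan says.** SAP 2.3 applies its analysis windows to trial endpoints generally and lists no exceptions. Position in time is a calendar-date difference without clock time: "Trial day = date of assessment - date of treatment". After screening, Table 2 selects the one record in each window that lies closest to the target day, and its note adds: "If two observations are equidistant to the target day, the first observation is used".

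Vital signs and ECGs are safety endpoints (SAP 2.2). At infusion visits each is measured twice. SAP Table 1, footnote 3 says of vital signs: "Conduct assessments pre-dose and up to 2 hours (+ 30 min) post-dose on Day 0". Footnote 7 says of ECGs: "Conduct assessment pre-dose, and within 2 hours (+ 30 min) post dose on Day 0". Both footnotes go on to list every later infusion visit through Week 84.

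SAP 3.2 defines baseline: "The baseline assessment will be the latest available valid measurement taken prior to the administration of Investigational Product". It adds that this will generally be Day 0.

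SAP 3.6.4.1 (vital signs) specifies: "The observed data at baseline and change from baseline for each measurement day will be summarized with descriptive statistics". It adds one figure: "A plot of average vital sign parameters will be presented over time". SAP 3.6.4.3 uses the same summary sentence for ECGs and then adds categorical QTcF tables ("Each QTcF value in a given patient will be grouped into 4 categories") and a summary of the investigator's interpretation. Neither section mentions a pre-dose or post-dose time point. Protocol 13.4.4.4 and 13.4.4.5 are no more specific.

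**The concern.** The two readings at an infusion visit share a date, so they share a trial day and lie equally far from the target. The tie rule then selects the earlier one, which is the pre-dose reading. The post-dose reading was scheduled in order to look for an effect of the infusion, yet it would be absent from the by-visit means.

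Safety is the primary objective, and post-infusion readings are the ones that could reveal an acute shift in blood pressure, pulse or ECG intervals. The gap is widest for vital signs, where the by-visit summary and the plot of averages are the only outputs specified and both would omit these readings. For ECGs it is partial, because the QTcF categories and the interpretation summary can still use post-dose tracings. A reader of the Day 0 row could also take a change of zero as evidence of no acute effect, when it would be an artefact of record selection.

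**Working it through.** The plan gives no figure on this point to reproduce. The check applies the rule as written and then counts the records affected.

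**Inputs.** Trial day definition, windows, target days and tie note: SAP 2.3 and Table 2. Visit allowances and the pre-dose and post-dose requirements: SAP Table 1 and footnotes 3 and 7. Baseline: SAP 3.2. Planned number treated, 120, and the assumption that at least 90 complete the primary phase: SAP 1.3.

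**Step 1: the tie.** Distance = |trial day − target day|. Take a Week 12 infusion given on Day 86. The pre-dose reading is at |86 − 84| = 2 and the post-dose reading at |86 − 84| = 2. The distances are equal whatever the visit day, because only the date enters.

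**Step 2: all permitted infusion-visit days.**

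| Visit | Allowance (days) | Permitted days |
|---|---|---|
| Day 0 | none | 1 |
| Weeks 12, 24, 36 | ±3 | 3 × 7 = 21 |
| Week 48 | −7/+14 | 22 |
| Weeks 60, 72, 84 | ±7 | 3 × 15 = 45 |
| Total | | 89 |

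Table 2 was coded as written and run on a same-date pair for each of these days. The pre-dose record was kept in 89 of 89 and the post-dose record in 0 of 89.

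**Step 3: Day 0.** The retained Day 0 record is the pre-dose reading, which is normally also the baseline. Change = pre-dose − pre-dose = 0.

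**Step 4: scheduled records per subject** (vital signs and ECGs have the same visits).

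- Eight infusions: screening 1 + 8 × 2 + Week 104 1 = 18. Post-dose share: 8/18 = 44.4%.
- Four infusions, secondary phase not entered: screening 1 + 4 × 2 + Week 48 1 + Week 56 1 = 11. Post-dose share: 4/11 = 36.4%.

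**Step 5: trial total per assessment type**, assuming one post-dose set per infusion.

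- All 120 receive four infusions: 120 × 4 = 480.
- All 120 receive eight: 120 × 8 = 960.
- Lower case: exactly 90 receive four, and the other 30 receive only one: 90 × 4 + 30 × 1 = 390.

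**Step 6: illustration.** A simulation of 120 subjects added a constant post-infusion shift of 2, 5 or 10 units. The shifts, a between-subject SD of 10 and a within-subject SD of 6 are assumptions. Under the rule, the Day 0 mean change was exactly 0 for every shift. Mean changes at Weeks 12 to 84 lay between −1.16 and +1.42 and bore no relation to the shift. The same-day post-minus-pre mean returned the assumed 2, 5 or 10 at each infusion visit. This shows the consequence of the literal reading; it is not evidence that the reading is the intended one.

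**The case against.** The strongest reply is that the literal reading was not intended. An equidistance note fits two visits on either side of a target day, such as Day 80 and Day 88 for Week 12, better than two readings on one day. PK concentrations are also trial endpoints with a same-date pair on Day 0, and SAP 3.5 plainly keeps both samples without claiming an exemption from 2.3. The vital sign and ECG sections refer to observed data on each measurement day and do not say one value per window. A Day 0 change fixed at zero itself suggests that nobody meant this.

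That stands as a plausible account of intent, and it is why the conclusion is limited to a literal reading. It does not remove the gap. PK keeps its post-dose sample because SAP 3.5 names that time; nothing equivalent is written for vital signs or ECGs. If the note does not cover same-day pairs, Table 2 still calls for one record and no rule says which. If both readings are pooled by day, pre-dose values dilute any post-dose shift. No reading yields a specified post-dose summary.

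The limits on impact also stand. Each QTcF value is categorised, the categories for increases above 30 and 60 msec are not tied to one record per window, and clinically significant post-treatment ECGs are summarised. Clinically significant findings can be reported as adverse events (Protocol 11.1.2), and several blood pressure and heart rate terms are events of special interest (SAP 3.6.2.1). What remains hidden is a mean shift too small to be judged significant in individual subjects. With no placebo infusion, such a shift could not be attributed to the drug with confidence. That limits its interpretation but is no reason to leave it unreported.

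Finally, 960 is a ceiling: the secondary phase is optional, and the plan itself assumes some subjects will not complete the primary phase.

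**Conclusion.** The concern holds. Applied exactly as written, SAP 2.3 omits the post-dose vital sign and ECG at every infusion visit where both readings exist, and normally sets the Day 0 change to zero. The omission covers 1 of the 2 records at each such visit. With 120 subjects, full attendance and one post-dose set per infusion, it amounts to 480 to 960 records per assessment type; the lower case in the working gives 390.

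The effect is confined to the by-visit mean-change summaries and the vital sign plot. It does not arise at visits without an infusion (Week 104 or 56, and Week 48 for subjects who do not continue) or where the pre-dose reading is missing. The data themselves are not lost.

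This should be fixed. Confidence is medium, because programmers may in practice separate pre-dose from post-dose values even though the SAP does not tell them to.

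**What to change.** - **SAP 2.3:** state that the one-record and tie rules apply within each nominal time point, with pre-dose and post-dose treated as separate time points. This alone removes the ambiguity.
- **SAP 3.6.4.1 and 3.6.4.3:** summarise post-dose values at each infusion visit, both as change from the same-day pre-dose value and as change from study baseline. The same-day change isolates the acute effect, which change from study baseline mixes with longer-term drift.
- **Vital sign plot:** show pre-dose and post-dose points separately.

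The cost is SAP wording and additional table rows. The readings are already scheduled, so no new data are needed.
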